**b. Gene therapy**

N/A

**7. Risks and Discomforts:**

fMRI

MRI is widely regarded as a safe, noninvasive procedure for visualization of brain tissue. The risks involved with fMRI are the same as those involved in standard anatomic MRI, since these three procedures rely on the same physical properties of brain tissue. This study will be performed on an FDA approved 3T scanner at the NIMH.

MRI at 3 Tesla is a routine clinical procedure, and issues regarding radio frequency deposition, time varying magnetic fields, and the static field at 3 Tesla do not require detailed discussion.

MRI at 7 Tesla (ultra high field strength) is less commonplace but becoming more so, as there currently are approximately 60 high field scanners in global operation. fMRI at 7T poses the minimal risk of vertigo-like sensations during movement in and out of the bore, but subjects in one study rated their discomfort of such sensations well below the length of scan session, which is the same for 7T as for 3T (Theysohn, et al. 2008). Furthermore, tissue heating from radiofrequency deposition is a minimal concern at small flip angles for fMRI at high fields (Gonzales-Castillo, et al 2011). Essentially, the risks of shocks in the scanner environment, with 7T as well as 3T, include heating of the electrodes with discomfort or burns. These risks, however, are actually less likely in the 7T scanner than

in 3T MRI scanner because in the 7T scanner the RF field does not extend to the whole body, as it does with the 3T.

### MRS

There is no known hazard to the exposure of magnetic waves during MR imaging. MRS does not introduce additional risks compared to fMRI (the gradient noise is much milder with MRS than MRI).

### Electric shocks: work-up

Electric shock poses minimal risk to participants. The shocks will be delivered through two disk electrodes located on one of the subjects' ankles or feet or wrist. Prior to testing, a shock work up procedure will be used to allow us to control for heterogeneity of skin resistance and pain threshold between participants and to administer a range of mildly painful stimuli in an ethical manner during the task itself. Shocks with step increases in amplitude will be administered up to a level tolerable to each participant, while participants will provide subjective ratings of shock intensity. The initial shocks are of mild intensity while participants familiarize with the setup. Up to three series of shocks will be administered (up to 20 shocks in total), as repeated escalation allows participants to adapt to initial anxiety about the shocks, since thereafter ratings are more consistent (Seymour et al., 2004, 2005). Participants are explicitly informed of their right to discontinue the research without consequence at any point during the consent process and then again following the sample shock procedure. Our experience is that over 95% of participants choose to participate in the experiment following the sample shock workup. Anticipation of the shock increases subjective anxiety and enhances physiological arousal.

### Electric shock within the MRI scanner

Introduction of electrical wires that are connected to the subject in the strong magnetic field of the scanner may constitute an additional risk. The main risk associated with administering shocks is the introduction of electrode wires directly in the RF- (radio frequency) field of the magnet. Wires will not be exposed to the radio frequencies induced in the RF head coil. The shock stimulator equipment will be outside the magnetic area, and a plastic and copper cable is taken through the wall for connection to the subject electrodes. To eliminate the possibility that electrode wires will enter the RF-field from subject movements, shock electrodes will be attached to either the foot or ankle region. Similarly, electrodes for skin conductance recording in the scanner will be attached to the sole of the other foot. Area between the wires will be minimized by twisting the wires together, and coiling of the wires will be prevented by inspection prior to each session (i.e., wires run without loops). Studies employing wires for electrical stimulation (e.g., Disbrow et al., 1998) or for psychophysiological measurement (skin conductance; Büchel et al, 1998; LaBar et al., 1998 etc) have been reported in the literature.

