#### *v. Study procedures*

This protocol includes an fMRI study of cognition and emotion without threat of shock (2.5 hours; 90 minutes in the scanner), an fMRI threat of shock study (2.5 hours; 90 minutes in the scanner), an MEG cold pressor study (1.5 hours), and an MEG threat study (2.5 hours), an alprazolam/threat MEG study (5-6 hours, 2 sessions), and an alprazolam/threat fMRI/MEG/MRS study. An additional telehealth consenting visit may be added to each during the pandemic. The alprazolam studies have been completed. Participants will not necessarily complete all these components of the study but will initially be recruited for one component and then invited to participate in additional components as needed. MEG and alprazolam studies will only recruit healthy subjects. Healthy volunteers and patients may undergo the wrist shock task in 7T or 3T fMRI machine.

After initial telephone screening, individuals who appear to qualify for inclusion will be invited for an in-person screening at the NIH.. On the screening day, subjects will be asked to sign an informed consent for screening protocol 01-M-0254. A medical and psychiatric history will be taken and a physical exam will be conducted. Subjects will also be asked to fill out various questionnaires of mood and anxiety. Subjects will complete informed consent for protocol 02-M-0321 prior to study procedures. Questionnaires may be administered on the day of the study procedures through the Clinical Trial Survey System (CTSS)/ Clinical Trials Database (CTDB).

We estimate that 1186 healthy subjects and 686 patients will be needed: about 30 subjects per experiment (in at least 6 studies), so that high-quality data is acquired from at least 15-20 subjects per experiment, with enough subjects to account for

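### The MRI shock-safety text relies on foot or ankle electrodes to keep wires from moving into the RF field, but section 4 permits a wrist shock task in both scanners

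*Combined protocol and SAP*

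**What the plan says.** Section 7, under Electric shock within the MRI scanner, treats wires lying directly in the scanner's RF field as the chief hazard of giving shocks there. Its answer to movement is electrode position. So that there is no chance that "electrode wires will enter the RF-field from subject movements, shock electrodes will be attached to either the foot or ankle region". No exception is given, and the next sentence assumes the same layout: "Similarly, electrodes for skin conductance recording in the scanner will be attached to the sole of the other foot".

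The same paragraph makes commitments that do not depend on electrode site:
- "Wires will not be exposed to the radio frequencies induced in the RF head coil"
- "The shock stimulator equipment will be outside the magnetic area"
- the wires are twisted together to reduce the area between them
- "coiling of the wires will be prevented by inspection prior to each session"

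Section 4.v (Study procedures) says: "Healthy volunteers and patients may undergo the wrist shock task in 7T or 3T fMRI machine".

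Three other places provide for the arm without naming a setting. Exclusion criterion 12 concerns nerve-compression syndromes in studies with wrist electrodes. The shock work-up text in section 7 includes the wrist among the sites. The unconditioned-stimulus text in section 4 includes the forearms.

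**The concern.** The foot or ankle rule and the wrist permission cannot both be followed in one scanning session. Someone who reads only the safety section would conclude that shock leads in the scanner run to the leg, and that movement of those leads into the RF field has been dealt with. Someone who reads section 4.v would conclude that a wrist task in the magnet is allowed.

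At stake is whether the stated protection against the hazard that the protocol itself ranks first covers everything the protocol allows. Section 6 also rests its view that the shock device poses no serious risk on the device being used as the protocol describes. For electrode placement in the scanner, the protocol describes two incompatible uses. No outcome, analysis or sample size is affected.

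**Working it through.** No arithmetic applies: the point depends on no sample size, power or error rate. The check is a comparison of the text.

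1. **Which hazard is meant?** Electrode wires in the RF field (section 7, Electric shock within the MRI scanner). The sentence at issue deals with one route to it, namely wires brought in by the participant's movement.

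2. **Which measure is tied to that route?** Foot or ankle placement, and nothing else. The other measures work differently:
   - Twisting the wires reduces the area between them.
   - Inspection before the session prevents coiling.
   - Keeping the stimulator away from the magnet concerns the equipment, not the lead on the participant.
   - The statement that wires will not be exposed to head-coil RF is a commitment to a result. The only means given for securing it while the participant moves is the foot or ankle position.

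3. **Does the wrist permission reach the scanner?** Yes. Criterion 12 and the work-up text could be read as covering MEG or laboratory sessions only. Section 4.v cannot, because it names the 7T and 3T fMRI machines, and it covers healthy volunteers as well as patients.

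4. **Is a movement control for wrist leads given elsewhere?** None was found. The fMRI paragraph of section 7 discloses that the risks of shocks in the scanner "include heating of the electrodes with discomfort or burns" and compares the two scanners. Disclosure and comparison are not a control on where a wrist lead goes.

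5. **How often does it arise?** Not stated. Section 4.v says the wrist task may be used, none of the sub-study descriptions in section 4 ties its shocks to the wrist, and no session count is given.

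Steps 1 to 4 establish that the movement control stated for the scanner does not cover a procedure permitted in the scanner. Step 5 means that the frequency is unknown.

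**The case against.** The best reply is that the wrist site is plainly deliberate. Section 4.v permits it expressly for both scanners, and both criterion 12 and the work-up text provide for it. On this reading nobody faces two equal rules; the general text in section 7 was simply not updated. That is the likelier history, and it bears on which fix to choose. It does not remove the conflict: no clause says which statement prevails, and the safety section still claims elimination by a measure that wrist sessions do not use.

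A second reply is that much of the hazard stays covered, since the head-coil commitment, the remote stimulator, the twisted wires and the inspection bind wrist sessions too. This stands, and it narrows the gap to one item: how a wrist lead is kept out of the RF field while the participant moves.

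Two stronger readings are tempting but not supported.

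- A reader might infer that the problem is worse at 3T, because section 7 says heating and burns are less likely at 7T "because in the 7T scanner the RF field does not extend to the whole body, as it does with the 3T". That sentence compares electrode heating and burns between scanners; it does not address entry of wires by movement. If the field is whole-body at 3T, leads at any site may already lie within it, so entry by movement is less distinctive there. The text does not support ranking one scanner above the other on this point.
- A reader might cite the section 4 paragraph on shock-induced motion, with its jerk-like reaction, as evidence that wrist leads will move. That paragraph concerns head position and image artefact. It says nothing of the arm or the leads.

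**Conclusion.** The point holds as an internal inconsistency in a safety control, and it should be fixed. For wrist shocks in the scanner, neither the claim to have eliminated entry of wires by movement nor the control behind it applies, and no substitute is stated.

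Its size cannot be put as a number. The permission extends to both populations and both field strengths; the number of wrist sessions is not given.

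A reader might go further and infer that wrist placement is unsafe, or that participants have been exposed to harm. The documents do not show either. The conclusion rests on the current protocol text alone and assumes that nothing outside it supplies the control. A local MR safety procedure may already do so, in which case the correction is to state it in the protocol.

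**What to change.** Choose one.

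1. **Restrict the site.** Amend the sentence in section 4.v so that shocks given in the MRI scanner use the foot or ankle only. The cost is the loss of the wrist site in the scanner.

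2. **Keep the wrist and give it its own control.** This suits the protocol better if the wrist is intended, as it appears to be. In section 7, confine the elimination statement to foot or ankle placement. Allow the wrist only with a stated lead-routing safeguard that keeps wrist leads out of the head-coil RF field during movement, confirmed by MR safety review for the 3T and the 7T scanner separately. The cost is a protocol amendment and that confirmation.

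Under the second option, prefer lead routing to arm restraint. Section 4 rejects a bite-bar because restraining participants that way adds baseline anxiety and muscle stress. Arm restraint could raise the same difficulty in a study that manipulates anxiety.

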### MEG

MEG is a noninvasive procedure to measure brain responses by recording magnetic fields and electrical potentials outside the head with sensors,. No known risks is associated with this procedure.

### Eyetracking in MEG

The unit is a passive monitoring system, and nothing is attached to the subject. There are minimal risks associated with this procedure.

### Startle stimulus

The auditory stimuli that will be used in the startle studies are 40-ms duration 103 dB white noise. Auditory startling sounds of much higher intensities are frequently used in startle studies. Sounds of higher intensities and longer duration are also widely used in aversive conditioning in human subjects, where they serve as unconditioned stimuli. The short duration (40 ms) of these sounds minimizes risk of hearing loss (Blumenthal et al., 2005). In addition, a white noise is safer than a pure tone. The PI has been involved in similar studies and collaborations involving over 1000 of subjects with no adverse reactions. The auditory stimulus may trigger a migraine.

### Cold Pressor test

The cold pressor test is a simple, safe and reliable procedure, widely used to determine cardiovascular reactivity, pain perception and stress response in healthy subjects, as well as in clinical conditions such as hypertension or depression (Velasco et al. 1997, Kelly et al. 1998). There are no known risks associated with the cold pressor procedure.

### Psychophysiological recording

The psychophysiological measures that will be obtained are non-invasive, requiring the administration of no needles, drug, or dyes. Little discomfort is expected. During electrode placement, the possibility of skin irritation from contact with the saline electrode paste exists. However, this is unlikely since the salt concentration of the paste is similar to that of human sweat. The risk is equivalent to that of an EEG recording.

### Alprazolam

Alprazolam (Xanax™) is a benzodiazepine widely used in the treatment of anxiety disorders or for the short-term relief of anxiety symptoms. For chronic treatment of anxiety disorders, the PDR (2000) recommends a daily dose up to 4 mg, given in divided doses. Plasma levels are proportionate to the dose given. Peak concentration in the plasma occurs in one to two hours following administration. For dose 0.5-3.0 mg, peak levels of 8.0 to 37 ng/mL are observed. Mean plasma elimination half-life is 11.2 hours. Contraindications include sensitivity to benzodiazepines. Side effects in patients using chronic alprazolam include insomnia, drowsiness, fatigue, headache, involuntary movement, nausea, and memory difficulties. Besides its effect on anxiety in clinical populations, alprazolam has also been frequently used to test the effects of benzodiazepines on experimental anxiety at doses of 0.5 and 1 mg. This study has been completed.

### Emotional pictures

The emotional pictures will be selected from a set of standardized stimuli that are frequently used in psychophysiological and brain imaging studies of emotions (Lang, Ohman, & Vaitl, 1988). Because the intensity of these pictures might make some people uncomfortable, their contents will be fully described to the subjects before participation

in the study. In addition, a debriefing will be conducted to assess whether subjects are distressed or negatively affected by the pictures and in need of psychological supports by a clinician. A clinician will then talk to them and will follow up with a call.

#### Delayed Treatment (patients only)

Although participants will not be taken off any medication for the purposes of this study, we will only include those patients who are not currently taking any psychotropic medications, with the exception of PTSD participants only. Thus patients included in this study may be at risk of increased symptoms because of the absence of psychopharmacologic treatment. During the initial psychiatric assessment, clinical staff will inform patients that delaying psychopharmacological treatment may increase their risk of increased symptoms and that such treatment is readily available at mental health care providers outside of the NIH. PTSD participants may continue on antidepressants and benzodiazepines.

Storage/sharing of data and samples: There is minimal risk that data or samples could be identified. To minimize this risk, data and samples that are shared will be de-identified. Data and samples will be sent with a code. This linking code will be kept at the NIH.

Grip force measures: This measure is not expected to increase risks in human subjects. Gripping hard may cause muscular fatigue or soreness but is not expected to increase risk of injury or harm to the subject. The fatigue or soreness is expected to be mild and self resolve without treatment.

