C) A third hypothesis is that while anticipation of unpredictable shocks will reduce GABA concentration, leading to low peak frequency of stimulus-induced gamma oscillations in the occipital cortex and increases BOLD response, the benzodiazepine alprazolam will have the opposite effect (increased GABA, leading to high peak gamma frequency and decreased BOLD signal).

D) A fourth hypothesis is that under threat of shock, prefrontal executive control regions will be less successfully engaged by patients with high anxiety or MDD than healthy controls. Further, we predict that both patient groups will recruit the cortical and subcortical limbic regions (e.g., amygdala, bed nucleus of stria terminalis (BNST), and insula) to a greater extent than healthy controls when under threat of shock. In contrast to anxiety patients, MDD patients will additionally recruit subgenual/rostral ACC in response to threat.

E) In the PTSD hippocampus investigation, we hypothesize that the hippocampus and dorsolateral prefrontal cortex (dlPFC) will play a key role in the effect of anxiety on BPS Task performance and that participants with PTSD will exhibit amplified pattern separation deficits. We also hypothesize that pattern separation deficits will be associated with PTSD symptom severity in the dentate gyrus as indicated in the high-field 7-Tesla resting state scan. Lastly, we hypothesize that the PTSD group (vs. no-PTSD) will have increased hippocampal-dependent spatial memory deficits on the Morris water maze (MWM) task.

F). We hypothesize that during the AAST paradigm, participants will exhibit enhanced neural responses to the avoidance cue during the threat-of-shock condition, within areas of the medial prefrontal cortex, amygdala, and striatum. Furthermore, we hypothesize that participants with PTSD will exhibit reduced medial prefrontal cortex responses during threat contexts, and elevated avoidance behavior. Lastly, we hypothesize that individual differences in avoidance behavior will be associated with the magnitude of task elicited neural activity within the medial prefrontal cortex, amygdala, and striatum.

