**c. *Exclusion criteria***

Subjects will be excluded from the study if they meet the following exclusion criteria:

- 1) Clinically significant organic disease, e.g., cardiovascular disease.
- 2) Clinically significant abnormalities in physical examination.
- 3) Any medical condition that increases risk for fMRI (e.g. pacemaker, metallic foreign body in eye).
- 4) History of any disease, which in the investigators' opinion may confound the results of the study, including, but not limited to, history of organic mental disorders, seizure, or mental retardation.

- 5) Have a current diagnosis of alcohol or substance abuse ACCORDING TO DSM IV CRITERIA
- 6) Have a lifetime diagnosis of alcohol or substance dependence ACCORDING TO DSM IV CRITERIA.
- 7) Unless subject is enrolled as a patient, subjects should not have current Axis I psychiatric disorders as identified with the Structured Clinical Interview for DSM-IV, non-patient edition (SCID/NP).
- 8) If a healthy volunteer, past bipolar depression and any history of psychosis or delusional disorders.
- 9) If a healthy volunteer, first degree relative with history of psychotic disorder such as schizophrenia or bipolar disorder.
- 10) Healthy participants may not be on psychotropic medications.
- 11) Pregnancy, i.e., a positive β-HCG urine test conducted prior to each experiment session.
- 12) Current or past history of cubital tunnel syndrome or carpal tunnel syndrome for shock studies that use the wrist for placement of electrodes. Cubital tunnel and carpal tunnel syndrome are exclusionary only for diagnosis on same arm as electrodes and are not exclusionary for studies that place shocks on ankles or feet.
- 13) Reynauds syndrome for the cold pressor test experiment
- 14) Color blindness (for the active avoidance task only)

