#### *Time perception* (Healthy N=50)

Participants will be asked to judge for how long stimuli (emotional faces: fearful, happy, neutral, taken from a standardized battery, NimStim OR simple shapes) remained on the screen. They then have to make a button press denoting the relative duration of these stimuli, compared to durations they learned.

*Memory* (Healthy N=80; Patient N=90 from each patient group, 20 of which will overlap with the patients in the Perception experiments because they will be run in the same session) These memory tasks will also include the below noted groups.

Morris Water Maze task (Healthy controls without war-zone exposure N=30, Healthy controls with war-zone exposure N=30, PTSD from war-zone exposure N=30) In one procedure, participants navigate a virtual reality water maze with a joystick to learn the location of an escape platform. Participants perform a series of trials. On some trials, the platform is visible to allow them to encode its location, and on other trials, they must retrieve its location by using spatial information in the virtual environment.

Behavioral Pattern Separation Task (Healthy controls without war-zone exposure N=30, Healthy controls with war-zone exposure N=30, PTSD from war-zone exposure N=30) The BPS Task consists of two phases; in the first encoding phase, participants assign an “indoor/outdoor” verdict to pictures of neutral objects. Following this encoding phase, participants complete a memory test (i.e., the retrieval phase), where they must identify pictures of neutral objects as “Old”, “Similar”, or “New”. One-third of the objects in the retrieval phase are “Old” or exact repetitions of the objects presented in the encoding phase; one-third of the objects are “New”, not presented during the encoding phase; and one-third of the objects are perceptually “Similar” to the objects presented during the encoding phase, but not identical (i.e., lures). We are particularly interested in the

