lure object responses and the rates at which participants correctly identify these as “Similar”, avoiding the inclination to identify these as “Old”. Identifying the lure objects as “Old” (i.e., overgeneralization) is likely driven by pattern completion processes. In contrast, discriminating the lure objects from the “Old” objects requires a distinct representation—a hallmark of pattern separation. The encoding and retrieval phases will be presented under safe and threat contexts (i.e., threat of unpredictable shock) to investigate the role of experimental threat on pattern separation and pattern completion processes.

In a separate procedure, subjects will be asked to remember verbal and nonverbal stimuli. These stimuli consist of words, pictures, letters or spatial locations in series of stimuli. Participants will be instructed to remember one, two, or three stimuli back from the current stimulus on the screen (n-back). Subjects will also be asked to simply view the stimuli (without responding) as well as remember words or International Affective Picture System (IAPS) pictures that they were presented with previously after a short delay. IAPS pictures include both positive and negative images. Examples of pleasant pictures include baby faces, ice cream, puppies, fireworks, and erotic pictures. Examples of unpleasant pictures include car accidents, guns, surgery, snakes, tumors, and bleeding faces. Subjects will be told that these pictures distressing and they will be reminded of the option to withdraw from the experiment at any time.

*Resting State* (Healthy N=40; Patient N=60 from each patient group, all of which will overlap with some of the patients in the Memory and Perception experiments because they will be run in the same session) This task will also include (Healthy controls without war-zone exposure N=30, Healthy controls with war-zone exposure N=30, PTSD from war-zone exposure N=30)

Subjects will be asked to lie still with their eyes open and stare at a fixation cross for 6-9 minutes. They will be asked to remain as still as possible and not fall asleep. During a resting state run, subjects will not engage in any task. However, on some rest runs, they will be under the threat of a shock they have already experienced. On other runs, they will be told they will not receive a shock.

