All experiments except for those that include patient groups will use within-subject designs, such that each participant will experience each comparison condition of interest (note: this does not imply that ALL subjects will participate in ALL procedures, just that the procedures in which they elect to participate will include the conditions necessary to perform the intended analyses). Experiments that include patients will operate both within-subject and between-subject designs; the within-subject factors being the experimental conditions, and the between-subject factor being subject group (patient or healthy control).

*b. Criteria for significance*

For voxel-wise analyses on normalized whole brain data, we will control false positive rates per map at  $\alpha=.05$ , using random-effects models (see e.g., Zarahn, 2000; Zarahn et al., 2000; Pine et al., 2001; 2002).

*c. Power analysis*

Sample size of 15 subjects with good quality data (no major artifacts or other problems) is usual for previous published studies on activation of limbic structures, such as Phelps et al. (1999; N=12), and Whalen et al. (1998; N=10). Although power computations are possible for ROI analyses using conventional statistical tests in which average BOLD signal intensities are treated as dependent variables, because the current study constitutes a pilot experiment that has not been previously performed, the mean and standard deviation of the changes in BOLD responses that will be obtained using the proposed methods are not known. In general, with sample sizes as small as  $n=10$  and for alpha = .05 (two-tailed), power exceeds .80 to detect effect sizes of 1.2 in one pre-specified brain region. Fortunately, most fMRI studies of neurobiologically meaningful task-associated changes in BOLD signal document larger effects than this. For patient subtypes, (i.e., GAD, SAD, panic, phobia, PTSD, and MDD) an  $N$  of 30 will be targeted for each study. This larger sample size will provide us with a greater range of symptom severity in order to conduct correlation analyses with regional brain activity and it will buffer against potentially higher rates of attrition (excessive motion, symptom-related dropout) in our psychiatric samples.

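### PTSD participants may stay on antidepressants and benzodiazepines while every control is unmedicated, and no analysis uses medication, so the PTSD memory contrasts cannot separate PTSD from a benzodiazepine effect

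*Combined protocol and SAP*

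**What the plan says.** **Medication rules.** Section 7, Delayed Treatment, admits only patients who take no psychotropic drugs and then makes one exception: "PTSD participants may continue on antidepressants and benzodiazepines". Section 11.d repeats that the exception is for PTSD only. For controls, Section 3.c says: "Healthy participants may not be on psychotropic medications". Section 3.b (item 3) classes the war-zone-exposed comparators as healthy controls, so the bar covers them too.

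**Analysis.** For experiments with patients, Section 10.a gives "the between-subject factor being subject group (patient or healthy control"). Section 10 also mentions correlations with symptom severity, and gender and trait anxiety among healthy volunteers. It mentions medication nowhere. Controls are matched on age, sex, race and IQ (Section 4.ii). Medication history is listed at screening (Section 4.iii), but no analysis uses it.

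**Hypotheses and groups.** Hypothesis E (Section 2) predicts that "the PTSD group (vs. no-PTSD) will have increased hippocampal-dependent spatial memory deficits on the Morris water maze (MWM) task", and also predicts worse pattern separation in PTSD. The water maze groups are: "Morris Water Maze task (Healthy controls without war-zone exposure N=30, Healthy controls with war-zone exposure N=30, PTSD from war-zone exposure N=30"). The pattern separation groups have the same sizes. Hypothesis F adds that "participants with PTSD will exhibit reduced medial prefrontal cortex responses during threat contexts".

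**Known drug effect.** The Alprazolam paragraph of Section 7 states: "Side effects in patients using chronic alprazolam include insomnia, drowsiness, fatigue, headache, involuntary movement, nausea, and memory difficulties".

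**The concern.** Medication can occur on one side of the PTSD contrast and never on the other. The war-zone-exposed controls separate trauma exposure from PTSD. They cannot separate drug from PTSD, because none of them may be medicated.

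The memory scores are the clearest case. The side effect listed for a benzodiazepine, memory difficulties, points the same way as the deficit that hypothesis E predicts. If the PTSD group does worse on the water maze or on overall pattern separation, the planned contrast credits this to PTSD. A benzodiazepine effect confined to that group would give the same result. A finding of hippocampal dysfunction in PTSD could then be partly or wholly a finding about treatment.

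**Working it through.** **Inputs from the plan.** 30 participants per group (Section 4.iv); alpha 0.05, two-tailed (Section 10.c). The plan has no power calculation for any PTSD v control contrast, so there is no figure of its own to reproduce here. Its paired calculations do reproduce with the noncentral t: d_z = 0.5 needs 34 and d_z = 0.6 needs 24, as stated.

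**Assumed inputs.** m is the number of the 30 PTSD participants whose score is shifted by a drug, and d is the shift in SD units. The documents give neither.

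**Bias.** With no true PTSD effect, the expected group difference is (m/30) × d. For m = 15 and d = 0.5 it is 0.5 × 0.5 = 0.25 SD.

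**Rejection rate.** Two-sample t-test, 30 v 30, unit SD, no true PTSD effect, 100,000 simulated trials per cell:

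| Affected (m of 30) | d = 0.3 | d = 0.5 | d = 0.8 |
|---|---|---|---|
| 0 | 5% | 5% | 5% |
| 5 | 5% | 6% | 7% |
| 10 | 7% | 9% | 16% |
| 15 | 9% | 15% | 30% |
| 22 | 13% | 28% | 58% |

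If only benzodiazepine users are affected, the upper rows are the more natural ones.

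**Safe-threat differences.** For pattern separation, "The encoding and retrieval phases will be presented under safe and threat contexts", so a within-person difference can be formed. Active avoidance is likewise measured as a safe-threat difference. With m = 15, unit SD in each context and an assumed correlation between contexts of 0.3, 0.5 or 0.7:
- An equal 0.5 SD shift in both contexts cancels, and rejection stays at 5%.
- A 0.5 SD shift under threat only gives about 12%, 15% and 22%.
- A shift of 0.5 SD under threat and 0.25 SD under safety gives about 7%, 8% and 9%.

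These contrasts are exposed only if the drug acts differently under threat and safety.

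**Precision of an unmedicated contrast against 30 controls.** The detectable effect is the d that gives 80% power, with noncentrality d / √(1/n + 1/30). The 95% half-width is t × √(1/n + 1/30).

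| Unmedicated PTSD (n) | Detectable effect | 95% half-width |
|---|---|---|
| 30 | 0.74 SD | 2.00 × 0.258 = 0.52 SD |
| 15 | 0.91 SD | 2.02 × 0.316 = 0.64 SD |
| 8 | 1.15 SD | 2.03 × 0.398 = 0.81 SD |

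The last row goes with m = 22, the case behind the 58%.

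**The case against.** **The evidence on memory is thin.** It is a side-effect list for one benzodiazepine, in the risk text of a completed sub-study, with no frequency or size. No passage says that antidepressants impair memory. This stands. The mechanism is documented for benzodiazepines only, and the rejection rates rest on assumptions.

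**The group-factor sentence is generic.** It covers all patient experiments and does not even distinguish the two control groups, so it is not a full model for the PTSD studies. That is fair, but no other text supplies a medication analysis.

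**The memory scores are not named outcomes.** Section 9 lists fMRI and MEG as primary and does not name the water maze or pattern separation scores. Hypothesis E still predicts a group difference on them.

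**Drug effects on threat responses.** A reader might infer that all PTSD contrasts, active avoidance included, are confounded to the same degree. The documents do not support that. An equal shift cancels, and Section 1.1 reports that startle to a discrete threat cue was insensitive to benzodiazepines in four experiments. That evidence concerns startle, not avoidance or BOLD, and not the unpredictable-shock context used for pattern separation. It leaves the question open.

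**Medication is already recorded.** A reader might infer that the data are missing. They are not: history is listed at screening, which runs under a separate protocol not available here. Section 11.f also treats entering treatment as a reason not to invite a patient back. However, for someone who returns within a year of the diagnostic interview it describes only a short check of symptoms and functioning, and the plan lists no medication record at the session.

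**Allowing medication is an ethical and practical choice.** It is, and nothing here requires changing it. Unmedicated participants may differ in severity, so restricting to them may bring in another difference. That limits the remedy but does not remove the problem.

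**Conclusion.** The concern holds for the Morris water maze and overall pattern separation scores. As planned, any drug effect in the PTSD group is counted as PTSD, and for benzodiazepines the listed effect runs in the hypothesised direction. For safe-threat differences and the PTSD v control part of active avoidance it is secondary and uncertain. It does not reach the resting-state association with symptom severity or the parts of hypothesis F that are not group contrasts.

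The size is unknown. With an assumed 0.5 SD shift, rejection under no PTSD effect is about 6% to 9% for 5 to 10 of 30 affected and about 15% for 15 of 30. A reader might take the 58% cell as the expected error, or conclude that a PTSD deficit would be a drug artefact. The documents support neither, because they do not say how many participants are medicated or how large any effect is. What is established is that the planned analysis cannot tell the two explanations apart. The change is worth making because it is cheap.

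**What to change.** 1. At each session, confirm and record current psychotropic drug, dose and last intake for PTSD participants.
2. In Section 10, pre-specify group for the PTSD contrasts as control, PTSD unmedicated and PTSD medicated, separating benzodiazepine users where numbers allow. A plain medication covariate is not enough: no control is medicated, so it is estimated only within the PTSD group.
3. Report PTSD v war-zone-exposed control for all PTSD participants and for unmedicated ones, plus medicated v unmedicated PTSD, each with a 95% interval.
4. Attribute a group difference to PTSD itself only so far as the unmedicated estimate and its interval support it. Otherwise describe it as a difference between PTSD as treated and unmedicated controls. A rule based on the two estimates having opposite signs would not serve. With a 0.5 SD shift in 15 of 30, it flags under 2% of the false positives (about 0% at 10 of 30, 16% at 22 of 30).

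**Cost.** A short record at each session and a few added estimates; no one stops medication. The added contrasts are imprecise: detectable effects rise to 0.91 SD at 15 v 30 and about 1.15 SD at 8 v 30. Medicated v unmedicated at 15 v 15 has a half-width of 2.05 × √(1/15 + 1/15) = 0.75 SD. Because severity may also differ between the subsets, the unmedicated contrast is a sensitivity check and not proof.
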